β -cell function will be preserved. This would make puberty a potential treatment period to target prevention of T2DM.

DESIGN

Participants:

1. 104 Obese participants:
 - a.) BMI \geq 95th percentile
 - b.) Tanner stage II – III at baseline
 - c.) Age \geq 9 years
 - d.) Absence of impaired glucose tolerance (IGT), impaired fasting glucose (IFG) or T2DM, as determined by oral glucose tolerance test (OGTT)

Exclusion criteria:

See Specific Aim 1

Approach:

All obese subjects who are recruited will be randomized after Study Visit 1 to receive metformin or placebo. The 52 participants randomized to the placebo group will then also serve as the obese subjects for the longitudinal observational studies of Specific Aim 1 (Please see Fig 2 for further clarification). In other words, 52 obese participants will be included in both Specific Aims 1 and 2, in order to minimize the total number of participants needed. Randomization will be stratified by: 1) Family history in a first degree relative with T2DM or no family history and 2) BMI between the 95th and 99th percentile or BMI greater than the 99th percentile. The extended release metformin will be started at 500 mg daily for one week and then increased by 500 mg a week until the target dose of 2000 mg a day is attained. The extended release preparation allows patients to take the medication once a day to promote improved adherence and is better tolerated. All obese participants will receive standard lifestyle counseling, focusing primarily on dietary improvements and increased physical activity. The total treatment period will be two years to include, on average, the most resistant stages of puberty. In order to monitor metformin compliance closely, the participants will come in for monthly pill-counts. In addition, each participant will be provided with a pill dispenser and a calendar to record each dose that is taken to assist with and track compliance. Furthermore, parents will be encouraged to remind the participant to take his/her medication. Participants will be given a point each time they bring in their pill bottle, whether or not they have been compliant, and will be eligible for an extra gift card for every 6 points they obtain. Our group has extensive experience in maintaining metformin compliance in this population (52). Tanner staging, anthropometric measurements and lifestyle counseling will also be performed at quarterly visits.

The CTRC study visit described previously for Study Visit 1 will be repeated twice more: at the end of this treatment period (Study Visit 2) and six months after the treatment is stopped (Study Visit 3). IVGTT, DEXA, abdominal fast MRI and soleus muscle NMR will also be repeated. We anticipate that the majority of patients will be Tanner stage V (T5) at the end of the 2-year treatment period, as the average time from the onset of breast development until menarche is 2-3 years. If T5 has not been reached after two years, the treatment will continue until the individual is at T5. Follow-up visits for Tanner staging will occur quarterly.

The final visit (Study Visit 3) will be to determine whether insulin sensitizing treatment will result in persistent improvement in insulin sensitivity and insulin secretion, even after treatment is stopped. The subjects will again be given a 3-day standard macronutrient diet and will fast overnight prior to admission. Only the IVGTT and anthropometric measurements will be performed at this study visit.

Specific Methods:

Screening laboratory studies: ALT, AST, electrolytes, fasting lipids, CBC, BUN and urinalysis.

Laboratory studies drawn at Visits 1, 2 and (for obese subjects only) 3: sex steroids, c-reactive protein (CRP), interleukin-6 (IL-6), adiponectin and fasting lipids. Sex steroids (free testosterone, estradiol,

androstenedione and DHEAS) will be drawn in order to confirm or refute previously found associations between sex steroids and IR. Inflammatory markers and other factors that have been associated with IR will also be drawn at this visit, including c-reactive protein, interleukin-6, adiponectin and fasting lipids (LDL, HDL and triglycerides).

Anthropometric measurements: Height, weight, waist-to-hip ratio, and supine abdominal height are measured by standard techniques.

Oral Glucose Tolerance Test: Glucose and insulin drawn at fasting (0), and at 30, 60, 120 and 180 minutes after ingestion of glucola (1.75g/kg, max 75g)

Dual-energy X-ray absorptiometry (DEXA Scan): Body composition will be measured supine using the DEXA technique on the pediatric CRC and will be used to derive fat-free mass (92). This technique relies on the absorption of dual electron wavelengths for the assessment of body fat, lean tissue, and bone mineral density.

Fast Magnetic Resonance Imaging (MRI) sequence: Rapid MRI will be used to assess hepatic fat fraction by the modified Dixon technique, previously described (56). In this technique, in- and out-of phase images of the liver will be obtained using a 1.5 Tesla magnet. The subject will be placed in a supine position on the body coil. The scan parameters include relaxation time = 9.3 ms (in-phase) and 7.3 ms (out-of-phase), echo time = 4.2 ms (in-phase) and 2.1 ms (out-of-phase), flip angle = 30 degrees, slice thickness = 10 mm, field of view = 32 x 16 cm, matrix size = 256 x 128, and number of excitations = 8. Four image slice pairs (in- and out-of-phase) will be obtained through the liver. Fat fraction will be calculated from the mean pixel signal intensity (SI) using the formula: Fat fraction = $(SI_{inphase} - SI_{outofphase}) / (SI_{inphase} + SI_{outofphase})$. A single slice at the level of the umbilicus will be used for determination of abdominal adipose distribution. Fast spin coil with a flip angle of 70 degrees, repetition time = 120 ms, echo time = 1.6 ms, field of view = 36 x 27 cm, slice thickness = 5.0 mm, matrix = 256 x 128, and number of excitations = 1.

Nuclear Magnetic Resonance Imaging (NMR): [name], of UCHSC radiology, will perform soleus NMR on a 3.0 T whole-body MRI scanner (GE Medical Systems, Waukesha, WI). The subject is positioned in the MR magnet feet first, prone, with the soleus muscle centered in the extremity coil. Scout images (usually T1-weighted) position the volume-of interest (usually 2cm x 2cm x 2cm), to avoid regions of gross adipose and vascular structures. Spectroscopy acquisition is performed using the PRESS pulse sequence without water suppression (TR/TE = 2000/24 ms, 64 averages, total acquisition time 2 minutes), and analyzed by SAGE spectroscopy analysis (GE). The water peak is fit as a Lorentzian line using Marquardt routine, and subtracted from the spectrum. The remaining peaks (creatinine and choline) are then fit using the Marquardt routine. IMC and EMC triglyceride peaks (1.3 and 1.5 ppm, respectively) are obtained from the fit results, corrected for T1 and T2 relaxation, and expressed as a percentage of the water content (96). Subjects need to hold reasonably still during the scan and cannot weigh >300 lbs.

All of the preceding imaging studies avoid radiation exposure and are regularly available at our institution.

Standard macronutrient diet: 3 days of a diet composed of 55% carbohydrates, 30% fat, and 15% protein will be provided by the CTRC. This diet is the standard used by the UCHSC Center for Human Nutrition prior to insulin clamps or VO2max testing as variations in dietary intake affect insulin sensitivity.

Frequently sampled IVGTT: Prior to admission, they will be given a 3-day standard macronutrient diet by the CTRC and will also be restricted from intense exercise for seven days. They will be asked to fast overnight before admission. An IV catheter will be inserted into each arm. At times -15 and zero, glucose and insulin will be drawn. Participants will then be infused with 0.3g/kg of 25% dextrose over 60 seconds. Glucose and insulin will be sampled from the contralateral arm at times 2, 3, 4, 5, 6, 8, 10, 12, 14, 16, 19, 22, 25, 30, 35, 40,

50, 60, 70, 80, 90, 100, 120, 140, 160, and 180 minutes. Bergman's minimal model program will be used to calculate insulin sensitivity (S_I), insulin secretion (AIR_{glucose}) and DI (DI).

Sample size calculation: A recruitment goal of 52 participants per group has been set (normal weight controls, obese controls, obese on metformin—a total of 156 participants). Assuming a 30% drop-out rate, this will give a final sample size of 30 per group. Power was run in PASS (NCSS Software; Kayesville, UT) and was calculated using a one-way ANOVA with a two-sided significance level of 0.05. Variability of the estimates was based on data available in an article by Buchanan et al. (57) in which IVGTT insulin sensitivity was measured in high-risk Hispanic women at baseline and 3 months for a placebo (n=109) and a troglitazone group (n=108). The 3-month change was -0.17 and 1.16 min^{-1} per $\mu\text{U}/\text{ml} \times 10^{-4}$, for the placebo and treatment groups, respectively. Assuming a correlation of 0.5, the estimated overall standard deviation of the 3-month change for both the placebo and treatment groups was 1.85 min^{-1} per $\mu\text{U}/\text{ml} \times 10^{-4}$. For this study, we assume similar variability and expect the 2-year change for the obese control and metformin groups to also be similar to those seen in the Buchanan et al. groups. The 2-year insulin sensitivity change in normal controls is expected to be similar to the change seen in Ball et al. (11) for 46 white adolescents from Tanner II / Tanner III to Tanner V, which was 1.6 min^{-1} per $\mu\text{U}/\text{ml} \times 10^{-4}$. Therefore, with a standard deviation of 1.85 and expected 2-year changes of 1.16, -0.17 and 1.6 for the metformin, obese control and normal control groups, respectively, a sample size of 30 per group achieves 93% power to detect an overall difference between the groups.

Statistical analysis: All analyses will assume a two-sided test of hypothesis with an overall significance level of 0.05 and will be performed in either SAS v9.1.3 or above (SAS Institute, Inc., Cary NC) or Splus v7.0 or above (Insightful Corp, Seattle WA).

Simple descriptive statistics will be calculated for all variables (mean, median, standard deviation, minimum and maximum values for continuous variables; number and percentage of subjects for categorical variables). Linear regression will be used to compare 2-year change in insulin sensitivity, insulin secretion, and DI between groups for Specific Aims 1 and 2 (normal controls vs. obese controls and obese treated vs. obese controls). Potential confounders such as sex, 2-year change in percent body fat and 2-year change in BMI will be included in each model. In order to determine if the benefit of treatment persists beyond stopping treatment, the above analysis will be repeated on the change from baseline to 6 months post-treatment for the obese treated and obese control groups only. The mean change in each outcome from treatment stoppage to 6 months post treatment will also be calculated with 95% confidence intervals (CI) in order to assess maintenance of the level of each outcome. Although we are not powered for equivalence (to test the hypothesis that the 6-month change is equal to zero), the precision of the estimate and whether the difference is *clinically* significant will be evident from the 95% CI. A CTRC biostatistician will be available to consult on all matters of statistics.

Potential Difficulties and Limitations/Alternatives

In adolescence, the number of routine visits to the pediatrician tends to drop. Therefore, we foresee a potential difficulty in recruiting children who are just starting puberty. For this reason, we are including children who are both Tanner 2 and Tanner 3 at study entry. In both of these stages of puberty, insulin sensitivity has been shown to be significantly decreased when compared with Tanner 1 and Tanner 5. The length of time required for progression through puberty varies in individuals. It is important to measure the post-treatment insulin sensitivity in Tanner stage 5, because insulin sensitivity in Tanner 4 may not be significantly different from earlier in puberty and only at T5 insulin sensitivity returns to its pre-pubertal level. For this reason, if a subject has not reached Tanner 5 in two years, they will not have their Study Visit 3 until Tanner 5 has been attained. This means that some subjects may need to be treated for a longer period of time. However, in order to compare differences in insulin sensitivity after treatment is stopped between subjects, the interval from treatment stop (Study Visit 2) to post-treatment follow-up (Study Visit 3), should be consistent.

The natural recovery of pubertal insulin sensitivity may confound measurement of metformin effects on insulin sensitivity as puberty progresses. In order to control for this, we have included a placebo-controlled group and a group of normal weight controls. This will allow us to compare changes in insulin

sensitivity from baseline to the end of puberty between obese treated subjects and both normal-weight and obese subjects who have not been treated.

The length of this study and potential difficulty with attrition are also limitations of this study. To limit the number of participants lost to follow-up, we will maintain frequent contact with participants with quarterly visits for anthropometric measurements, monthly visits for pill-counts and phone contact at least once between these visits. In addition to these visits, the participants in the treatment group will be contacted by telephone at least monthly to inquire about medication side effects and to review changes in diet and exercise. Due to our involvement in the TODAY study and other trials of metformin, our staff are experienced with working on long-term projects with obese and T2DM adolescents, with excellent study retention out as far as four years.

Adverse effects of metformin include nausea, anorexia, diarrhea and vomiting. These adverse effects could potentially interfere with patient compliance. These effects have been shown to be reduced when the dose is titrated up slowly, as described in the Approach section of Specific Aim 2. Furthermore, in our experience with metformin, adverse effects did not result in decreased dose or significant patient attrition. Participants in the metformin group were only slightly less compliant than the placebo group in our blinded study of metformin in obese adolescents.

Finally, IVGTT is not the gold standard for measurement of insulin sensitivity. However, it has been shown to correlate well with the hyperinsulinemic-euglycemic clamp, which is the gold standard (21). It was chosen for this study as it is slightly less invasive and allows measurement of both insulin sensitivity and insulin secretion. In this population, which is as young as 9 years old and will be undergoing repeated measures, it is necessary to avoid time intensity and invasive procedures as much as possible. Therefore, it was felt that the benefits of IVGTT far outweigh the limitations in this protocol.

Summary

The temporary fall in insulin sensitivity that occurs during puberty is well-recognized. This is typically overcome by an increase in insulin secretion. However, certain risk factors for T2DM appear to affect the ability of the pancreas to compensate for this change in insulin sensitivity. The mechanism of pubertal insulin resistance remains poorly understood, with suggestions that GH/IGF-1 and sex steroids might play a causative role. Furthermore, little is known about the effect of obesity on decreased pubertal insulin sensitivity. If obesity is superimposed on the decreased insulin sensitivity of puberty, the resulting amplified insulin requirements may stress the β cells and lead to the development of T2DM. Thus, puberty may be a critical time to treat resistance, with the hope of preventing or at least delaying onset of β -cell failure. In the current proposal we will examine the longitudinal changes in insulin sensitivity, insulin secretion and body composition of normal weight and obese children during puberty. Furthermore, we will compare these changes in obese children with and without metformin treatment. These studies will increase our understanding of the contribution of puberty to the progression from obesity to IR and DM in adolescents. This knowledge will, in turn, allow to better target our preventive efforts.

Reference List

2. Type 2 diabetes in children and adolescents. American Diabetes Association. *Diabetes Care* 2000; 23(3):381-389.
6. Shulman GI. Cellular mechanisms of insulin resistance in humans. [Review] [28 refs]. *American Journal of Cardiology* 1999; 84(1A):3J-10J.

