Our unique combination of pediatric and adult endocrinology skills, laboratory expertise in insulin signaling, and clinical research experience in insulin sensitivity testing in obese youth make us perfectly poised to address these hypotheses. In addition, the use of a longitudinal study design will allow us to examine differences in percent body fat, body fat distribution and changes in BMI over time in the observational arm of the study. It also allows to examine whether treatment of obese children during this time can have beneficial effects on insulin sensitivity and secretion in the treatment arm. Enhancing our understanding of longitudinal changes of insulin sensitivity in obese adolescents and the response to metformin will help us identify potential interventions aimed at the prevention of T2DM.

The studies in this proposal will test the following hypotheses:

HYPOTHESES:

- 1. Obese adolescents, unlike normal weight controls, fail to improve insulin sensitivity at the end of puberty.**
- 2. Treatment of obese adolescents with metformin during puberty will help these individuals result in sustained improvement in insulin sensitivity at the end of puberty, decrease compensatory hyperinsulinemia, and preserve insulin secretion, thereby improving their disposition index (DI).**

To test these hypotheses, we propose to address the following Specific Aims:

SPECIFIC AIM 1 (Observational Arm):

- 1. To compare longitudinal changes in insulin sensitivity and secretion and their correlates in obese and normal weight adolescents during puberty.**
 - a. To compare changes in insulin sensitivity and secretion as measured by frequently sampled intravenous glucose tolerance test (IVGTT) from early puberty to puberty completion between obese and normal weight adolescents.**

- b. To compare changes in body composition, fat distribution, and inflammatory markers over time between these groups.**

Under this Specific Aim, insulin sensitivity and secretion will be measured by frequently sampled IVGTT in early puberty and at puberty completion in obese and normal weight adolescents. Changes in insulin sensitivity will be correlated with changes in inflammatory markers in all participants and body composition in a subset of these participants.

[figure not shown]
SPECIFIC AIM 2 (Treatment Arm):

- 2. To compare changes in insulin sensitivity and secretion and their correlates, in obese adolescents treated with metformin or placebo during puberty.**

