 - a. To compare changes in insulin sensitivity and secretion from early puberty to puberty completion between obese controls and obese adolescents treated with metformin.**
 - b. To compare changes in body composition, fat distribution, and inflammatory markers over time between these groups.**

Under this Specific Aim, obese participants from Specific Aim 1 will be randomized to receive placebo or metformin treatment during puberty. Frequently sampled IVGTT will be performed to measure insulin sensitivity and secretion in early puberty, at the end of puberty when treatment is stopped, as well as six months after treatment completion. Changes in body composition will also be measured in a subset of participants and changes in inflammatory markers will be measured in all participants at these time points.

The nested study design (Fig 1) will efficiently address four important knowledge deficits with a single recruited cohort: 1) Whether obese adolescents recover their pre-pubertal insulin sensitivity at the end of puberty; 2) The relationships between longitudinal changes in insulin sensitivity and changes in body composition in obese and normal weight youth; 3) Whether treatment with metformin during puberty can improve insulin sensitivity in obese adolescents to the level seen in normal weight pubertal adolescents; and 4) Whether treatment of obese adolescents during puberty will result in prolonged improvement of insulin sensitivity and secretion.

Fig. 1

B. BACKGROUND AND SIGNIFICANCE

Insulin Resistance and T2DM in Youth

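### Hypothesis 1 says obese adolescents fail to improve insulin sensitivity, but the only planned inference from baseline to Tanner V is a between-group contrast, which cannot tell no improvement from less improvement

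*Combined protocol and SAP*

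**What the plan says.** Section A states Hypothesis 1 as "Obese adolescents, unlike normal weight controls, fail to improve insulin sensitivity at the end of puberty". The account of the nested design in the same section lists as the first knowledge gap "Whether obese adolescents recover their pre-pubertal insulin sensitivity at the end of puberty". Both ask what happens within the obese group. Specific Aim 1, which is meant to test the hypothesis, is worded as a comparison of longitudinal changes between obese and normal-weight adolescents.

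The Statistical analysis paragraph in Section D says "Linear regression will be used to compare 2-year change in insulin sensitivity, insulin secretion, and DI between groups for Specific Aims 1 and 2", with the contrasts given as "normal controls vs. obese controls and obese treated vs. obese controls". On covariates it says "Potential confounders such as sex, 2-year change in percent body fat and 2-year change in BMI will be included in each model".

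For within-group information, the same paragraph begins "Simple descriptive statistics will be calculated for all variables" and lists mean, median, SD, minimum and maximum. It plans a mean change with a 95% CI for one interval only, from the end of treatment to six months later. There it adds that the study is not powered for equivalence and that the interval will show the precision and clinical importance of the change. No such interval is planned for baseline to the end of puberty.

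**The concern.** Hypothesis 1 has two parts: normal-weight adolescents improve, and obese adolescents do not. A contrast between the two mean changes tests neither part alone. It would come out the same way if obese adolescents improved, but by less.

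Failure to improve is a claim of little or no change. The authors handle such a claim with a confidence interval for the six months after treatment, but not for the period that Hypothesis 1 concerns. Section A links failure to regain insulin sensitivity to β-cell stress and progression towards type 2 diabetes, so the difference between not improving and improving less affects how the observational arm is read.

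**Working it through.** **Inputs** (Sample size calculation, Section D): SD of change 1.85; expected two-year changes 1.6 (normal weight), -0.17 (obese control) and 1.16 (metformin); two-sided 0.05; stated final n of 30 per group. I also use n = 36, because 52 recruited per group less the stated 30% drop-out is 52 × 0.7 = 36.4. The true obese change is my assumption and is varied. I read the two-year change as the change from baseline to the Tanner V visit. Units are those of S_I in the protocol.

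**The plan's own figure.** One-way ANOVA, three groups of 30. The grand mean is (1.16 - 0.17 + 1.6)/3 = 0.863. The squared deviations sum to 0.088 + 1.068 + 0.543 = 1.699. The noncentrality is 30 × 1.699/1.85² = 14.9 on 2 and 87 df, giving power 0.9345. The stated 93% is reproduced.

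**The contrast that serves Aim 1.** Two-sample t test, noncentrality (1.6 - x)/(1.85 × √(2/n)), where x is the true obese change. The standard error is 0.478 at n = 30 and 0.436 at n = 36.

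| True obese change x | Difference 1.6 - x | Significant, n = 30 | Significant, n = 36 |
|---|---|---|---|
| -0.17 (planned) | 1.77 | 95% | 98% |
| 0 | 1.6 | 91% | 95% |
| +0.2 | 1.4 | 82% | 89% |
| +0.5 | 1.1 | 62% | 70% |
| +0.8 | 0.8 | 38% | 44% |
| +1.0 | 0.6 | 23% | 27% |
| +1.16 | 0.44 | 15% | 17% |

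The probability passes 50% at x = 0.65 for n = 30 (0.65/1.6 = 41% of the normal-weight change) and at x = 0.73 for n = 36 (46%).

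**Sensitivity to the SD.** At x = +0.8 and n = 30 the figure is 72% for SD 1.2, 53% for SD 1.5, 38% for SD 1.85 and 28% for SD 2.2.

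**What a within-group interval would show.** The half-width is t × 1.85/√n:
- n = 30: 2.045 × 0.338 = 0.69. At the planned -0.17 the interval is -0.86 to 0.52.
- n = 36: 2.030 × 0.308 = 0.63. The interval is -0.80 to 0.46.

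The upper limits are 0.52/1.6 = 33% and 0.46/1.6 = 29% of the normal-weight change.

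**Why an interval and not a within-group p-value.** At a true obese improvement of +0.5, a one-sample test would detect it only 30% (n = 30) or 35% (n = 36) of the time. A non-significant within-group test would therefore not show failure to improve.

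**The case against.** The strongest reply is that the contrast is the right test for Specific Aim 1. The Aim is comparative, and the hypothesis itself is framed against normal-weight controls. A direct contrast is also sounder than calling one group improved and the other not on the strength of two separate tests. All of this stands, and the contrast should stay. It does not close the gap, because the hypothesis and the first knowledge gap say more than the Aim does.

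Second, the planned descriptive statistics may cover part of the need. If change in S_I is among the summarised variables, a reader could rebuild the interval from mean, SD and n. That is so, but the plan does not name this change, give its interval or say how it bears on the conclusion.

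Third, a reader might infer that the contrast would usually be significant whenever obese adolescents improve. The protocol's figures do not support that: at half the normal-weight change or more, significance is the less likely result (38%/44% at +0.8). Nor do the documents say that a significant contrast will be reported as failure to recover. That is a risk the plan leaves open, not a stated intention. The case for puberty as a treatment period also does not hang on this contrast alone, since the Specific Aim 2 rationale rests it on metformin preserving β-cell function.

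**Conclusion.** The point holds in a limited form. The planned inference for baseline to Tanner V cannot separate failure to improve from smaller improvement. Under the protocol's inputs, a significant contrast is more likely than not if obese adolescents truly improve by less than about 0.65 (n = 30) to 0.73 (n = 36), and becomes unlikely as their improvement approaches that of normal-weight controls.

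These figures assume a true normal-weight change of 1.6 and a common SD of 1.85, which the protocol takes from a three-month change in adult women with an assumed correlation of 0.5. A smaller SD raises the threshold and a larger one lowers it. They are also unadjusted: the planned model includes changes in BMI and body fat, and the documents do not allow their effect on the contrast to be quantified.

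**What to change.** Add to the Statistical analysis paragraph, in words such as these:

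> For obese controls and for normal-weight controls, the unadjusted mean change in S_I from baseline to Tanner V will be reported with its 95% CI. The between-group contrast remains the test of Specific Aim 1. If only the contrast is significant, the conclusion will be that obese adolescents improve less than normal-weight controls. Failure to improve will be described only in terms of the size of improvement that the obese-control interval excludes.

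The means should be unadjusted. Group means from the planned model would be set at common values of post-baseline BMI and body-fat change, and so would not describe what actually happened to the obese group.

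I would not build in a fixed margin without a clinical justification, since the documents offer none. A margin of 0.5, for example, would be met only about 48% (n = 30) or 56% (n = 36) of the time even if the planned -0.17 were exactly true.

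The change needs no extra visits, data or participants. Its cost is that the conclusion may be weaker than Hypothesis 1 as worded, because an interval of about ±0.63 to ±0.69 cannot exclude small improvements.
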